This randomized controlled trial will be conducted in real-world mental health settings providing services to clients within the Massachusetts Department of Mental Health (DMH) community-based system of care, the Mental Health Center of Greater Manchester (MHCGM) in Manchester, NH, the Greater Nashua Mental Health Center of Community Council (GNMHCCC) in Nashua, New Hampshire, and the Community Mental Health Affiliates (CMHA) in New Britain, CT. A total of 144 young adults with SMI and overweight/obesity (BMI ≥ 25) will be recruited from the MHCGM, GNMHCCC, and CMHA, as well as from sites within DMH to participate in a randomized controlled trial. The study will be referred to as the “Fit Forward Lifestyle Trial for in Young Adults.” Participants will be randomized 1:1 to PeerFIT or to Basic Education in fitness and nutrition supported by a wearable Activity Tracking device (BEAT), resulting in approximately 72 clients randomized to PeerFIT and 72 clients randomized to BEAT. Recruitment will occur on a rolling basis with the PeerFIT group intervention starting once at least 2 new people have been randomized to PeerFIT. Thus, we will run open PeerFIT groups in which up to 18 new members are welcome to join at any time during the life of the group. The BEAT individual intervention will begin as soon as 2 participants are randomized to that intervention. This rolling recruitment process combined with open PeerFIT groups is an adaptation to the study design intended to reduce the participant burden of waiting to start the intervention until a full cohort of participants is recruited, which typically takes many months.

INTERVENTION AND CONTROL CONDITION

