BMI	Weight (kg)/height (m) ²	Interviewer	✓	✓	✓	BMI: Body Mass Index
Cardiorespiratory Fitness	6-MWT	Interviewer	✓	✓	✓	6-MWT: 6-Minute Walk Test
Lipid profile	Cardio Check	Interviewer	✓	✓	✓	Cardio Check Testing Device
Hemoglobin A1c	A1c Now	Interviewer	✓	✓	✓	A1c Now Testing Device
Waist circumference	Tape measure	Interviewer	✓	✓	✓	Guilick tape measure
Blood pressure	Cuff	Interviewer	✓	✓	✓	OMRON Hem-907 devic
Dietary Measures						
Sugar sweetened beverage consumption	Early Trials	Self-report	✓	✓	✓	Measure adapted from the EARLY trials
Eating away from home	Early Trials	Self-report	✓	✓	✓	Measure adapted from the EARLY trials
Daily meal patterns	Early Trials	Self-report	✓	✓	✓	Measure adapted from the EARLY trials
Physical Activity Measures						
Sedentary behaviors	Early Trials	Self-report	✓	✓	✓	Measure adapted from the EARLY trials
Vigorous exercise	IPAQ	Self-report	✓	✓	✓	IPAQ: International Physical Activity Questionnaire
Psychosocial Measures						
Exercise Self-Efficacy	ESE	Self-Report	✓	✓	✓	Self-efficacy for exercise scale
Peer Social Support (PeerFIT arm only)	SPS	Self-Report	✓	✓	✓	SPS: Social Provisions Scale
Group Climate (PeerFIT arm only)	GCS-Q	Self-Report	✓	✓	✓	GCS-Q: Group Climate Questionnaire
Group Cohesion Scale (PeerFIT arm only)	GCS	Self-Report	✓	✓	✓	GCS: Group Cohesion Scale
Perceived Social Support (both arms)	MOS	Self-Report	✓	✓	✓	MOS-Social Support Survey
Other Questionnaires						
Demographics	CDI	Self-Report	✓	✓	✓	Client Demographics Instrument
Psychiatric Diagnosis	Med Record Dx	Staff	✓			Review of participant's chart
Medication Use	Med List	Self-Report	✓	✓	✓	Self-reported medications
Smoking and Alcohol Use	BRFSS	Self-Report	✓	✓	✓	BRFSS: Behavioral Risk Factor Surveillance System
Weight history	WHQ	Self-Report	✓			Weight History Questionnaire
Self-weighing	Self-weigh	Self-Report	✓	✓	✓	Self-weighing
Depressive Symptoms	CES-D	Self-Report	✓	✓	✓	Center for Epidemiologic Studies Depression Scale
Sleep Quality	PSQI	Self-Report	✓	✓	✓	Pittsburgh Sleep Quality Index
Neighborhood Environment	PANES	Self-Report	✓			Neighborhood Environment for Physical Activity
Technology use	CTUS	Self-Report	✓			Consumer Technology Use Survey
Treatment Covariates						
WM Attendance	WMS Log	LC		✓	✓	Adherence to weight management sessions
GE Attendance	GES Log	LC		✓	✓	Adherence to group exercise sessions
BEAT Attendance	BEAT Log	PM				
Fitbit Adherence	Device	Fitbit App		✓	✓	Proportion of days participant wore the device

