International Physical Activity Questionnaire (IPAQ) – vigorous questions only: The IPAQ is a measure of physical activity used to assess days in the past week and number of hours or minutes in one of those days doing physical activity across four domains: work, transportation, caring for the home/family, and recreation. Each domain is divided into categories including time spent walking, being moderately active, and being vigorously active. The IPAQ also assesses time spent sitting in a “usual” week day and weekend day in the past week.¹⁹ For this study, we are only collecting time spent being vigorously active.

Variables and Measures for Aim 2 (Mediators)

Exercise Self-efficacy: The Exercise Self-efficacy measure will be used to assess participants’ confidence in their ability to persist in exercising in various situations. Five items represent the following the following areas: negative affect, negative affect, resisting relapse, and making time for exercise. Respondents rate their confidence on a five-point Likert scale ranging from 1 = “Not at all Confident” to 5 = “Extremely Confident.” Scores range from 1 to 25 and higher overall scores suggest higher exercise self-efficacy.

Social Provisions Scale: We will measure participants’ level of perceived peer group support from the PeerFIT intervention with the 24-item Social Provisions Scale (SPS).¹⁰ The SPS consists of six subscales to measure the availability of social support: emotional support or attachment, social integration, reassurance of worth, tangible help, orientation and opportunity for nurturance. The items are scored on a 4-point Likert scale from 1 = *strongly disagree* to 4 = *strongly agree* as it pertains to relationships with group members. Higher scores indicate greater perceived support from group relationships. The SPS has documented reliability and validity within social networks of young adults,¹¹ and has been used to study the influence of group dynamics on weight loss outcomes in a prior weight loss study.¹²

The Group Climate Questionnaire – Short form (GCQ-S) will be used to assess how participants regard the climate of the PeerFIT group intervention.¹³ The GCQ-S consists of three subscales: engaged, conflict, and avoiding. The 12-item self-report questionnaire assesses the positive working group atmosphere, anger or tension of the group, and behaviors that indicate avoidance of personal responsibilities of group work by the members.

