Power Analysis for Aim 1. Assuming a range of within-person, across time correlations (0.1-0.7), with 144 participants (72 per arm), there will be 80% power, at the two-sided 0.05 significance level, to detect a difference between arms in slope of at least 0.030-0.052 SD units per month, or equivalently, 0.36-0.62 SD units over 12 months. If SDs of weight, BMI, and 6-MWT are similar to those observed previously (approximate weight SD 60, BMI SD 9, and 6-MWT SD 350) with the InSHAPE intervention and active control, these standardized effect sizes are equivalent to difference between arms of 21.6-36.0 lbs, 3.20-5.40 BMI units, and 6-MWT of 126-210m over 12 months. With attrition, power will be slightly lower, or equivalently, detectable differences slightly larger. To provide information on detectable differences if maximum attrition is experienced we also provide detectable differences assuming data from only 115 participants (80% of proposed sample size). In this case, the detectable difference increases to 0.034-0.059 SD units per month or 0.41-0.70 over 12 months yielding detectable weight of 24.6-42.0 lbs, BMI of 3.69-6.30, and 6-MWT of 143-245m over 12 months. True power/detectable difference likely lies in between for 144 vs. 115 participants. In the InSHAPE trial, 38% of participants in the active control arm and 51% of participants in InSHAPE achieved a clinically significant change in cardiovascular risk reduction. Because InSHAPE likely had a strong intervention effect with one-on-one personal fitness training and a gym membership for the active control, we estimate that percentages achieving clinically significant change in cardiovascular risk reduction in this study will be 20% for BEAT and 40% for PeerFIT. Assuming these proportions, there will be 86% power to detect a difference between arms in cardiovascular risk reduction, assuming measures of this outcome at 2 time points and within-person correlation of 0.5. With maximum attrition, the power is reduced to 77%.

Specific Aim 2 (Mechanism of Action): To test the mechanism hypotheses, parallel process latent growth curve models will be fit within a structural equation model (SEM) framework. These models allow for testing mediation of the treatment effect on weight and fitness by changes in self-efficacy (H2a) and peer social support (H2b). It is hypothesized that PeerFIT will have a greater effect on the change over time (slope) of

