self-efficacy than BEAT, and this change in self-efficacy will impact change in weight and fitness over time (slopes). PeerFIT is hypothesized to have a greater effect on peer social support slope than BEAT, and this change will also impact the change in outcomes. The product of coefficients (coefficient associated with path between treatment and mediator x coefficient associated with path between mediator and outcome) will be estimated along with bias-corrected bootstrap confidence intervals to determine the significance of the effect.

Power Analysis for Aim 2. The mechanism to be tested is the indirect effect of treatment on changes in weight and fitness (outcomes) through changes in self-efficacy and changes in peer social support (proposed mediators). The power for detection of the indirect effect depends on the size of each effect in the pathway.

The proposed parallel process growth curve analysis proposes mediation of the individual latent slopes, so power is computed at the individual-level although the individual-level latent slopes are estimated using data from observed mediators and outcomes measured at three time points (0, 6, and 12 months) improving precision. To compute power for detecting the mediated effect, we use results of a simulation study conducted by MacKinnon et al. In the simulation, indirect effects composed of effect of treatment on mediator and mediator on outcome were varied in size and significance was repeatedly tested via bias-correct bootstrap confidence intervals to obtain estimates of empirical power. This study showed that with 144 participants there will be approximately 80% power to detect a significant effect if the mediated effect is made up of two effects that are halfway between small and medium as defined by Cohen (explaining about 6.3% of the variance). For example, if treatment explains at least 6.3% of the variance in changes in self-efficacy, and changes in self-efficacy explain at least 6.3% of the variance in changes in weight, then there will be 80% power to detect this effect via bias-corrected bootstrap confidence intervals constructed around the indirect effect of treatment on changes in weight. If at least one of the effects (treatment to mediator or mediator to outcome) is larger (at least a medium effect explaining 13% of the variance), power is greater than 80%.

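### H2b cannot be tested as planned: the only measure labelled peer social support is collected in PeerFIT alone, and the both-arm MOS is never assigned to it

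*Combined protocol and SAP*

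**What the plan says.** Section 3.6.5, Specific Aim 2, plans parallel process growth models that allow a test of "mediation of the treatment effect on weight and fitness by changes in self-efficacy (H2a) and peer social support (H2b"). The contrast is between arms: "PeerFIT is hypothesized to have a greater effect on peer social support slope than BEAT". The test statistic is the product of the treatment-to-mediator and mediator-to-outcome coefficients, with a bias-corrected bootstrap interval. The section names no instrument for peer social support.

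Table 1 has one row with that label, the SPS, marked "Peer Social Support (PeerFIT arm only"). Section 3.6.2 says the SPS captures "perceived peer group support from the PeerFIT intervention with the 24-item Social Provisions Scale", with items answered "as it pertains to relationships with group members". BEAT has no such group. The Design Summary says "The BEAT individual intervention will begin as soon as 2 participants are randomized to that intervention", and the description of the comparison condition has monthly one-to-one sessions.

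The MOS Social Support Survey sits under the same Aim 2 mediators heading in Section 3.6.2. Table 1 marks it for both arms at 0, 6 and 12 months. It is described as perceived availability of support in four components, with a total and subscale scores.

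On power, the plan states that "with 144 participants there will be approximately 80% power to detect a significant effect" when each path explains about 6.3% of variance. The worked example is for the other mediator: "if treatment explains at least 6.3% of the variance in changes in self-efficacy".

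**The concern.** A mediation test that starts from randomization needs the mediator in both arms. A reader who follows the plan's own label takes the SPS and has no BEAT data for the first path. One of the two Aim 2 mechanism hypotheses then cannot be run as written. What remains is an association within PeerFIT between support and outcome. Participants who engage more may both feel more supported and lose more weight, so that association is open to confounding and is not a randomized effect on the mediator. A reader who turns to the MOS instead must choose the construct and the score without guidance from the plan.

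**Working it through.** **Inputs.** 144 participants randomized 1:1, about 72 per arm (Design Summary). SPS in PeerFIT only, MOS in both arms (Table 1). 6.3% of variance per path (Power Analysis for Aim 2). Attrition of at most 20%, leaving 115 (Handling of Missing Data; Power Analysis for Aim 1). The documents give no alpha for Aim 2, so a 95% interval is assumed.

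**1. The plan's power figure.** Simulation of a single-mediator model with equal arms coded ±1, no direct effect and a bias-corrected bootstrap (1,000 resamples, 2,000 trials, Monte Carlo error about 1 point).
- Path size: √(0.063/0.937) = 0.259. For treatment to mediator this is a standardized difference of 2 × 0.259 = 0.52.
- N = 144: 82%, against the plan's approximately 80%.
- One path raised to 13%: 89%, consistent with the plan's claim of more than 80%.
- N = 115: about 70%. The Aim 2 text gives no figure for attrition.

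The 80% is therefore sound for a mediator observed in everyone.

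**2. Path a with the SPS.** The regression of the mediator on intercept and arm has rank 1 of 2 with 72 PeerFIT rows only, and rank 2 of 2 with 72 + 72 rows.

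**3. The whole model, using all outcome data.** Let M = i_m + aX + e_m and Y = i_y + bM + c′X + e_y, with X = 1 for PeerFIT. The 7 parameters are i_m, a, i_y, b, c′ and two residual variances.
- PeerFIT data give b, both residual variances, i_m + a, and i_y + c′.
- BEAT data, with M missing, add only the mean of Y, which is i_y + b·i_m. The BEAT variance of Y repeats what PeerFIT already gave.
- That makes 6 independent quantities for 7 parameters: rank 6 of 7. With M in both arms the rank is 7 of 7.
- The difference in mean Y between arms is ab + c′. Only this sum is known, so the mediated and direct parts cannot be separated.
- Fixing c′ = 0 gives rank 6 of 6, but ab then equals the whole arm difference by construction. Mediation is assumed, not tested.

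The model above uses observed variables. The same argument applies to latent slopes, because the mediator slope in BEAT is never observed.

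**4. What the SPS can support.** Only the mediator-to-outcome association within PeerFIT. At 6.3% of variance its power is about 58% with n = 72, and about 49% with n = 58 (72 × 0.8 = 57.6).

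**5. Illustrations for the MOS, on assumed values that the documents do not give.**
- If treatment explains 4% or 2% of mediator change instead of 6.3%, power at N = 144 is 68% or 43%.
- Take no treatment effect on support, and subscale correlations of 0.5 to 0.8. One pre-named score gives a false mediation result in 6–8% of trials; free choice among five scores (total plus four subscales) gives 14–21%.

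The conclusion does not depend on step 5.

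**The case against.** The strongest reply is that the plan never says H2b uses the SPS. Section 3.6.5 names no instrument, and the link rests on a row label. The MOS is under the mediators heading, is marked for both arms beside three rows marked for PeerFIT only, and is the one support measure there that can run the planned test. It may well have been included for that purpose.

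Part of this stands. Both-arm support data exist, so the problem can be repaired, and the test is impossible only with the SPS. But the heading does not assign the MOS to H2b, since it also covers group climate and group cohesion. Table 1 labels the MOS as perceived social support, not peer social support, and no score is chosen.

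It is also fair that the SPS, as described, is not specific to health behavior either. The clearest difference between the two is that the SPS asks about fellow group members. The MOS has some related content (friends to have fun with) but is broader. A gap from the Section 2 hypothesis would therefore exist with either scale.

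The 6.3% assumption is unsupported for both mediators, so that weakness is not particular to the MOS. The visit table in Section 11 labels BEAT a group intervention, against the other descriptions. That does not help, because the SPS is still not collected in BEAT.

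**Conclusion.** The concern holds. With the measure that carries its name, H2b as a PeerFIT-versus-BEAT mediation test is not identified (rank 6 of 7, no SPS data in about 72 BEAT participants), and the power of about 80% does not apply to it. This is a failure of identification, so a larger sample would not cure it. With a both-arm mediator the test is identified, with about 82% power at N = 144 and about 70% at N = 115, conditional on 6.3% of variance per path. The conclusion rests on Table 1's arm restriction being applied as written and on no constraint on the direct effect. It should be fixed before analysis. Its reach is limited: Aim 1 is untouched, and so is H2a, whose self-efficacy measure carries no arm restriction.

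**What to change.** Before analysis, issue a dated amendment that does one of the following:
1. Name the MOS as the H2b mediator, state the single score to be used (total or one named subscale), and declare that the construct becomes general perceived social support instead of peer support directed at health behavior.
2. State that H2b is not tested as mediation.

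In either case:
- Report the SPS, group climate and group cohesion scales only as associations within PeerFIT, not labelled as mediation.
- Limit the statement of about 80% power to a mediator measured in both arms, conditional on 6.3% of variance per path.
- Reconcile the month-0 SPS tick in Table 1 with the rest of the plan. Data Collection for Aims 1 and 2 schedules PeerFIT-specific interviews only at 6 and 12 months, and the Section 11 visit table puts the baseline assessment before randomization, when there is no group to rate. The day-1 baseline above Table 1 is stated for weight only.

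**Cost.** No new data collection, since the MOS is already collected in both arms at all three times. Option 1 is more than a wording change, because it alters a hypothesis while participants are enrolled; hence the dated, declared amendment. Its downside is that the MOS is less specific than the hypothesis, so the treatment effect on it may fall below the 6.3% assumed.

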3.6.2 Study Variables and Measures

Variables and Measures for Aim 1 (Primary Outcomes)

Primary Hypothesis (H1a). Weight will be measured as the change in body weight over time, and BMI will be calculated by the formula: Weight (kg)/Height(m)². Participants' weight will be measured in pounds (lbs.) on a flat, even surface with the use of a high-quality, calibrated professional digital scale, with the participant wearing indoor clothing and no shoes. Weight will be measured to the nearest 0.1 pound (lb) and duplicate measurements will be made. If the two measurements are more than 0.5 lbs apart, then a third measurement will be collected and the three measurements will be averaged. Scales will be calibrated quarterly by study personnel using standard weights. Weight will be measured in pounds (lbs) for ease of interpretation by participants. Weight will then be converted to kilograms (kg) for calculation of BMI. Participants' height will be measured to the nearest 0.1 cm using a calibrated, mobile stadiometer. The participant stands shoeless on a firm, level surface, with head in the horizontal (Frankfort) plane. Duplicate measurements of height will be collected. If the two measurements are more than 0.1 cm apart, then a third measurement will be collected and the three measurements will be averaged.

Cardiorespiratory fitness will be assessed by the 6-Minute Walk Test (6-MWT), a performance based measure of exercise capacity.⁷ After a baseline pulse has been obtained, participants are asked to walk a measured distance as far as they are able in 6 minutes. Standardized instructions are used to instruct the individual to reach a maximum comfortable pace without running. It is a reliable and valid measure of cardiovascular fitness in diverse populations. We have extensive RCT experience using the 6-MWT in persons with SMI.

Primary Hypothesis (H1b). Clinically significant cardiovascular risk reduction will be assessed by either a ≥5% weight loss or an increase in walking distance of >50 meters on the 6-MWT, both criteria are well-established indicators of clinically significant cardiovascular disease risk reduction.

Secondary Outcomes:

Lipids and A1c: We will test participants' non-fasting cholesterol, triglycerides, and A1c levels via a finger stick blood test done at the baseline assessment. The blood test requires only a tiny sample of blood (40 μ l) and is performed using the Cardio Check and A1c Now Polymer Technology Systems testing devices.

Blood Pressure: We will record blood pressure using the OMRON HEM-907 device, which records blood pressure using an oscillometric technique.

Waist Circumference: We measure waist circumference using an anthropometric tape, in a horizontal plane 1cm above the navel.

Dietary Measures

Sugar Sweetened Beverage Consumption: This tool measures the amount of sugar-sweetened beverages consumed by the respondent in a typical week. Specific beverages are included in the screener instrument to understand what types of beverages are commonly consumed and the consumption frequency of these specific beverages.

Eating Away from Home: The Eating Away from Home questionnaire is a self-report tool that assesses the frequency with which an individual consumes fast food, food prepared at a sit-down restaurant, food in an all-you-can-eat buffet, and food prepared at home. Respondents indicate their frequency of consuming food outside the home in the past 30 days (e.g. once per month, once per week, once per day). Respondents also report the number of days over the past week that they prepared breakfast, lunch, or dinner at home.

Daily Meal Patterns: Respondents are asked to indicate the number of times during a typical week they: (a) eat

breakfast; (b) eat a mid-morning snack; (c) eat lunch; (d) eat a midafternoon snack; (e) eat dinner; (f) eat an evening snack; (g) eat within an hour of bedtime, using either 0, 1-2, 3-4, 5-6, or 7 times.

Physical Measures

Sedentary Behavior Questionnaire (SBQ): The SBQ assesses the number of hours participants spend doing 9 behaviors (watching television, playing computer/video games, sitting while listening to music, sitting and talking on the phone, doing paperwork or office work, sitting and reading, playing a musical instrument, doing arts and crafts, sitting and driving/riding in a car, bus, or train).⁹ The 9 items are completed separately for weekdays and weekend. Response options are none, 15 minutes or less, 30 minutes, 1 hour, 2 hours, 3 hours, 4 hours, 5 hours, or 6 hours or more. The time spent on each behavior is converted into hours (eg, a response of 15 minutes was recoded as .25 hours). For the total scores of sedentary behavior, hours per day for each item are summed separately for weekday and weekend days. To obtain weekly estimates, weekday hours are multiplied by 5 and weekend hours are multiplied by 2 and these are summed for total hours/week.

International Physical Activity Questionnaire (IPAQ) – vigorous questions only: The IPAQ is a measure of physical activity used to assess days in the past week and number of hours or minutes in one of those days doing physical activity across four domains: work, transportation, caring for the home/family, and recreation. Each domain is divided into categories including time spent walking, being moderately active, and being vigorously active. The IPAQ also assesses time spent sitting in a “usual” week day and weekend day in the past week.¹⁹ For this study, we are only collecting time spent being vigorously active.

Variables and Measures for Aim 2 (Mediators)

Exercise Self-efficacy: The Exercise Self-efficacy measure will be used to assess participants’ confidence in their ability to persist in exercising in various situations. Five items represent the following the following areas: negative affect, negative affect, resisting relapse, and making time for exercise. Respondents rate their confidence on a five-point Likert scale ranging from 1 = “Not at all Confident” to 5 = “Extremely Confident.” Scores range from 1 to 25 and higher overall scores suggest higher exercise self-efficacy.

Social Provisions Scale: We will measure participants’ level of perceived peer group support from the PeerFIT intervention with the 24-item Social Provisions Scale (SPS).¹⁰ The SPS consists of six subscales to measure the availability of social support: emotional support or attachment, social integration, reassurance of worth, tangible help, orientation and opportunity for nurturance. The items are scored on a 4-point Likert scale from 1 = *strongly disagree* to 4 = *strongly agree* as it pertains to relationships with group members. Higher scores indicate greater perceived support from group relationships. The SPS has documented reliability and validity within social networks of young adults,¹¹ and has been used to study the influence of group dynamics on weight loss outcomes in a prior weight loss study.¹²

The Group Climate Questionnaire – Short form (GCQ-S) will be used to assess how participants regard the climate of the PeerFIT group intervention.¹³ The GCQ-S consists of three subscales: engaged, conflict, and avoiding. The 12-item self-report questionnaire assesses the positive working group atmosphere, anger or tension of the group, and behaviors that indicate avoidance of personal responsibilities of group work by the members.

Group Cohesion Scale: The Group Cohesion Scale-Revised (GCS-R) will be used to measure group cohesiveness within the PeerFIT group intervention. The GCS is a 25-item multidimensional scale rated 1=strongly disagree to 4 = strongly agree assessing domains such as interaction and communication, member retention, decision making, vulnerability among group members, and consistency between group and individual goals.¹⁴

Medial Outcomes Study Social Support Survey: The 19-item Social Support Survey will be used to assess four components of perceived availability of social support among participants in both conditions, including (1) Emotional support/Informational support, (2) Tangible support (including material support), (3) Positive social interaction (does person have friends that are available to have fun), and (4) Affectionate support (including loving and nurturing relationships). A total score and subscale scores are calculated. Higher scores indicate more social support.¹⁵

Participant Characteristics and Covariates

Demographic Characteristics: Demographic characteristics will be collected with a client demographics instrument (CDI) developed by our research group. Socio-demographic information will include age, sex,

gender, race/ethnicity, living situation, education, employment status, and other basic characteristics.

Psychiatric Diagnosis: Psychiatric diagnosis will be verified using the diagnosis in the chart at the agency providing mental health services.

Medication Use: Because medications can directly affect weight gain and level of physical activity, we will collect self-report data on the type of prescribed psychiatric medications (e.g., antidepressant, antipsychotic) and all other medications taken by participants at the time of assessment. We will ask participants to bring their current medications with them to the assessment appointment. The research interviewer will document all current prescription and non-prescription medications taken by participants. In addition, the research interviewer will review a list of psychiatric medications and FDA-approved and non-approved weight loss medication to assess whether participants are currently taking any of the medications on the list.

Smoking and Substance Use: We will use questions from the 2016 Behavioral Risk Factor Surveillance System to ascertain smoking history, frequency, quantity, and cessation attempts. We will also ask about participants' alcohol consumption during the past 30 days.

Weight History: We will use select items from the Weight History Questionnaire developed for the National Health and Nutrition Survey to assess both lifetime weight loss attempts and weight loss attempts made within the past 12 months.

Self-Weighing: Participants will be asked to report how often during the past month they weighed themselves with response categories ranging from: 0 = never weighed myself to 6 = several times a day.

Sleep Quality: The Pittsburgh Sleep Quality Index (PSQ) measures sleep quality and disturbance retrospectively over a 1-month period using self-reports.¹⁶

Depressive Symptoms: The Center for Epidemiologic Studies Depression Scale (CES-D) is a 20-item self-report scale that is sensitive and specific in detecting depressive symptoms.¹⁷ The CES-D has scores ranging from 0 to 60, where higher scores represent greater depressive symptoms. The CES-D has well-documented psychometric properties in psychiatric populations.

Technology Use: We will use the consumer mHealth survey to assess participants' use of the Internet, social media, mobile devices, mobile applications, and text messaging. This questionnaire was developed by our research team to assess how people receiving services at mental health centers use these technologies.

Treatment-related Covariates. The lifestyle coaches will document the number of weight management and exercise sessions attended.

Fitbit. In this study, participants in the PeerFIT intervention and BEAT comparison condition will use Fitbit Zip, Flex 2, or Inspire wearable activity tracking devices. Participants will receive instruction to wear this device daily and to focus on collecting steps each day and meeting daily step goals. We will collect data on the number of days enrolled in the study that participants wore their Fitbit. This will indicate whether participants used the device or not. Additionally, we will collect hours of sleep, as well as physical activity data which includes step count, activity intensities, metabolic equivalents, and energy expenditure. We have observed in our pilot work that increasing number of steps walked each day was significantly correlated with greater weight loss. Therefore, we intend to explore whether this relationship between number of steps and weight loss is consistent in this larger randomized controlled trial. Participants' Fitbit accounts will be connected by research staff to a secure data management platform called Fitabase. Fitabase allows researchers to analyze data from wearable and internet-connected devices. All data associated with the Fitbit devices will be assigned de-identified study IDs and linked to the Fitabase platform. Participants will have full access to their Fitbit accounts but will not be able to access Fitabase. By consenting to use the Fitbit device as part of this study, the participants also consent to allow the research team to register their Fitbit accounts on Fitabase. Only data collected during study participation will be shared with Fitabase and analyzed, and de-identified Fitbit accounts will be deleted from Fitabase 90 days following the completion of data analysis.

Facebook. In this study, participants in the PeerFIT intervention arm can choose to access a secret Facebook group. Participants will be encouraged to post content, comments, or like other participants' posts to help support the PeerFIT program goals focused on healthy lifestyle change. We will collect data on the frequency of use of the PeerFIT Facebook group. In our pilot study we observed that greater use of the secret Facebook group was associated with clinically meaningful weight loss, suggesting that participants who use the Facebook group may be more engaged in the overall PeerFIT program and may benefit from support and encouragement from each other. We plan to collect the frequency of use of the Facebook group measured as

the number of posts, number of comments, and number of likes for each participant over the 12-month study duration. This data will be exported directly from the secret Facebook group to an excel document at 6-months and 12-months follow-up.

4. Analysis

Describe any qualitative tests and measures as well as quantitative methods:

Data Analyses

Analysis of data from the RCT will answer research questions associated with Specific Aims 1 and 2. Careful examination of frequency distributions and descriptive statistics for all variables will precede inferential statistical analysis. When necessary due to high skew, transformations will be used to normalize continuous data, or continuous variables will be recoded to ordinal or dichotomous scales.

Evaluation of Randomization. We will evaluate the effectiveness of random assignment by comparing the PeerFIT and BEAT groups on baseline measures of demographic characteristics, key outcome variables, and key covariates using chi-square tests and t-tests.

Handling of Missing Data. Based on our prior studies we do not expect attrition to exceed 20% over 12 months. The proposed method of analysis, mixed effects models, have been shown to produce unbiased estimates of treatment effect in the presence of data that is missing completely at random or missing at random even when dropout differs between treatment arms.¹⁸ We will also perform sensitivity analyses to examine stability of treatment effect under different missing data assumptions as recommended in case data are not missing at random (i.e., missingness depends on the value of the missing observation).

